6.2.2 Handling, Storage and Accountability

1. The investigator or designee must confirm appropriate temperature conditions have been maintained during transit for all IP received and any discrepancies are reported and resolved before use of the IP.
2. Only subjects enrolled in the study may receive IP and only authorized study site personnel may supply or administer IP. Only IP with appropriate expiry/retest dating may be dispensed.
3. All IP must be stored in a secure, environmentally controlled and monitored (manual or automated) area in accordance with the labeled storage conditions and access must be limited to the investigator and authorized study site personnel.
4. The investigator, institution or the head of the medical institution (where applicable) is responsible for accountability, reconciliation and record maintenance (i.e., receipt, reconciliation and final disposition records).
5. Further guidance and instruction on final disposition of used and unused IP is provided in the pharmacy manual.

Refer to the pharmacy manual for detailed information regarding handling, storage and accountability of the IP.

6.3 Randomization and Blinding

This is an open-label study; however, enrollment, randomization and dispensation of IP will be performed via the interactive response technology (IRT) system. Prior to initiation of treatment, study site personnel will obtain the randomization number and treatment assignment from the IRT system. Specific IRT procedures will be described in the respective study manual.

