7. Blood and urine samples for pharmacokinetics of investigational product and possible metabolite(s) (if applicable) will be collected from every subject. A single pharmacokinetic blood sample will be collected at each of the following time points: prior to dose, approximately 10 minutes postdose, either approximately 30 or 60 minutes postdose and at the end of surgery. In cases where surgery is completed in less than 105 minutes, blood samples will also be collected at approximately 180 minutes after administration. Urine point sampling will be performed prior to dose and at the end of surgery (the end of surgery is an optional time point if a sample is available). For a detailed procedure of pharmacokinetic sampling, refer to the Sample Handling and Processing Manual.
8. Total urine volume of urine in the catheter bag will be calculated by dividing the weight of urine in the catheter bag by predefined density. Urine volume will be recorded in millimeters, and urine sample for pharmacokinetics of investigational product and possible metabolite(s) (if applicable) will be collected from the urine in the catheter bag to calculate Ae and Ae%. For a detailed procedure of total urine volume calculation, refer to the Sample Handling and Processing Manual.
9. The incidence of green discoloration of the urine will be recorded any time after dose administration. If it occurs, the color of urine will be assessed during surgery and every 120 minutes (\pm 30 minute window) after the end of surgery until it resolves or the subject is discharged, whichever is earlier. The start and stop date and time will also be recorded.
10. Surgeon evaluation for ureteral visualization includes incidence of anatomical visualization of the ureter(s), questions for the surgical benefit of ASP5354 and the Likert Scale for qualitative response about the intensity of fluorescence at the predefined time points during surgery.
11. Fluorescence images will be captured and recorded during the entire surgery and archived.
12. Postoperative vital signs and clinical laboratory tests will be collected within 2 hours after the surgery.
13. If a subject discontinues early from the study, day 7 outpatient visit procedures will be performed upon discontinuation.

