- The duration of anatomical visualization of the index ureter(s) will be from the first time of positive visualization to the last time point of positive visualization.
- Recorded images will be used to determine the signal background ratio (SBR).

The visualization data will be assessed by a Visualization Review Committee (VRC), consisting of the investigator(s) and the sponsor's medical representative. The VRC will be held at the following time points, but ad-hoc meetings may occur until the optimal dose is determined:

- 1) after the initial 3 subjects have completed the surgical procedures at each of the dose levels; and
- 2) then in increments of 3 subjects (up to a total of 15 subjects per dose level) for those who have completed surgical procedures at the expanded dose levels.

The visualization data for the subjects, at each interim time point, who completed the surgical procedure will be assessed to decide whether to:

- 1) expand a dose under evaluation;
- 2) stop a dose under evaluation in which case additional subjects would not be added to a dose level; or
- 3) define a dose as optimal.

Once the optimal dose is determined, the optimal dose cohort may continue enrollment up to the maximum 15 subjects.

The VRC assessment to stop, to continue or to define an optimal dose level will be based on the totality of the collected data, including but not limited to the following:

- 1) anatomical visualization, defined as positive visualization of the ureter at both 30 minutes after ASP5354 administration and at the end of surgery; or
- 2) fluorescence intensity based on the Likert Scale (0 to 3).

In the case where 2 doses perform equally, the lower dose may be selected.

Based on VRC review of the initial 3 dose levels, if none of the doses selected have visualization, then **CCI** and **CCI** dose levels will be added; if 1 dose selected has visualization, then the **CCI** dose level will be added. The **CCI** dose level will only be added if only the **CCI** dose level has visualization. For further details of the VRC, refer to the VRC charter.

If the investigator judges that anatomical visualization of ASP5354 is not sufficient for the subject at 30 minutes after administration, the investigator can proceed with surgery using other modalities for visualization.

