7 STUDY PROCEDURES AND ASSESSMENTS

7.1 Efficacy Assessments

7.1.1 Primary Efficacy Assessments

7.1.1.1 Anatomical Visualization of the Index Ureter(s) Using ASP5354

The investigator will select the index ureter (i.e., right or/and left) before surgery. The incidence of anatomical visualization of ureter(s) will be assessed at approximately 10, 20, 30, 45 and 60 minutes postadministration of ASP5354, and then every 30 minutes thereafter and/or at the last time point before removal of visualization instruments (end of surgery) by the investigator intraoperatively using a binary “Yes or No” question on the ability to visualize the ureter: “Can the ureter be adequately visualized with NIR-F”?

- If the answer to the question 30 minutes after ASP5354 administration and at the end of surgery = Yes, then anatomical visualization of the index ureter(s) was a success.
- All other cases will be handled as “Not a success”.

If the anatomical visualization of the index ureter(s) was not assessed, “Not Done” will be entered in the eCRF. However, in the only case that the anatomical visualization of the index ureter(s) was not assessed at 30 minutes after ASP5354 administration, the answer will be imputed as follows:

- If the answer at the nearest time points before and after 30 minutes both = Yes, then the answer to the question 30 minutes after ASP5354 administration will be imputed as = Yes.
- If the answer at the nearest time points before and after 30 minutes both = No, then the answer to the question 30 minutes after ASP5354 administration will be imputed as = No.
- All other cases will be handled as “Not Done” at 30 minutes after ASP5354 administration, and imputing will not occur.

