10.4 Study Organization

10.4.1 Visualization Review Committee

The visualization data will be assessed by the principal investigator/investigator and the sponsor's medical representative, who form the VRC. The VRC will be held at the following time points, but ad-hoc meetings may occur until the optimal dose is determined: 1) after the initial 3 subjects have completed the surgical procedures at each of the dose levels, and 2) then in increments of 3 subjects (up to a total of 15 subjects per dose level) for those who have completed the surgical procedures at each of the expanded dose levels. For further details on the VRC, refer to the VRC charter.

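### The dose assignment is open and the plan does not mask the surgeon who gives the subjective primary rating, although investigators also sit on the committee that picks the dose from those ratings

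*Protocol*

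**What the plan says.** **Assignment.** Protocol 6.3 (Randomization and Blinding) opens with "This is an open-label study". Before treatment, "study site personnel will obtain the randomization number and treatment assignment from the IRT system". The section does not say who may see the assignment and refers IRT procedures to a separate manual. SAP 2.3 repeats this.

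**Rating.** Under Protocol 7.1.1.1 the investigator answers, during surgery, "Can the ureter be adequately visualized with NIR-F". The word adequately is not defined. Footnote 10 to the Schedule of Assessments calls this the surgeon's evaluation. Success needs Yes at 30 minutes and Yes at the end of surgery; "All other cases will be handled as" not a success. The investigator also scores intensity on the Likert scale (7.1.2.1).

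**Dose selection.** Protocol 4.1 says: "The visualization data will be assessed by a Visualization Review Committee (VRC), consisting of the investigator(s) and the sponsor's medical representative". Section 10.4.1 repeats the membership ("who form the VRC") and names no independent member. The VRC meets after the first 3 subjects at each dose, then in steps of 3 up to 15. It decides on the totality of the data, and the two items listed are the visualization answers and the Likert score.

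**Independent reading.** None is described for the primary question. Surgery is recorded and archived, but the stated use of the images is the signal background ratio (7.1.2.3), which is exploratory. Section 12.1.7 mentions the records of a judgment committee outside the study sites, which has no role elsewhere in the documents.

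**The concern.** The primary objective is to find the optimal dose, and the primary endpoint is a judgement. A rater who knows the dose can be influenced by what that dose is expected to do, and such an influence differs between arms. Randomization does not protect against it, because it enters at the rating, after assignment. The Likert score and the duration of visualization depend on the same rater, so they offer no independent check.

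The same role then helps to choose the dose. With approximately 2 sites, the raters and the VRC investigators are probably much the same few people. The plan has no numeric threshold and no hypothesis test, and the tie rule is discretionary, so little else limits the effect of a few shifted ratings.

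**Working it through.** **1. The plan's own figures.** The maximum sample size reproduces: 3 × 15 = 45, and 6 × 15 = 90 with the added arms (SAP 3). No alpha, power or effect size is given. Masking the rater changes none of this.

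**2. Does any procedure need the rater to know the dose?**
- Dose modification is not applicable (Protocol 6.6).
- Continuation criteria and treatment discontinuation are not applicable (6.7, 8.1).
- The option to use other modalities at 30 minutes depends on judged visualization, not on dose (6.5.4).
- All arms receive one agent by one route, diluted before use (6.1) and given by site personnel (6.4).

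No stated procedure conflicts with withholding the dose during the rating, provided there is an exception for safety.

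**3. How little data the first look holds.** One changed outcome among 3 moves the observed rate by 1/3, or 33 points. For 3 of 3 the exact 95% lower limit is 0.025^(1/3) = 0.292, so the interval is 29.2% to 100%. For comparison, 12 of 15 gives 51.9% to 95.7%.

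**4. Illustration at one dose.** Assumptions, none from the documents: true success p = 0.60; one index ureter; a fraction b of No answers becomes Yes at this dose only. A failing subject can become a success in two ways:
- Upper case: only one time point was No, or both were No and the two flips are fully correlated. Observed rate = p + b(1 − p).
- Lower case: both time points were No and the flips are independent. Observed rate = p + b²(1 − p).

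| b | Case | Observed rate | Chance of 3/3 |
|---|---|---|---|
| 0 | – | 0.60 | 0.60³ = 0.216 |
| 0.25 | lower | 0.60 + 0.0625 × 0.40 = 0.625 | 0.625³ = 0.244 |
| 0.25 | upper | 0.60 + 0.25 × 0.40 = 0.70 | 0.70³ = 0.343 |
| 0.50 | lower | 0.60 + 0.25 × 0.40 = 0.70 | 0.343 |
| 0.50 | upper | 0.60 + 0.50 × 0.40 = 0.80 | 0.80³ = 0.512 |

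If both ureters are index, SAP 5.1 requires success in both. More answers may then have to flip, and the lower case is lower still.

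**5. Illustration for two equally good doses.** Let n subjects be rated at each dose, with true success p at both. At the favoured dose a failing subject is rated a success with probability 0.3, counted per subject, so q = p + 0.3(1 − p). The chance that the favoured dose looks strictly better is the sum over i > j of Bin(i; n, q) × Bin(j; n, p).

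| p | n | No bias | With bias |
|---|---|---|---|
| 0.5 | 15 | 0.428 | 0.745 |
| 0.7 | 15 | 0.421 | 0.641 |
| 0.9 | 15 | 0.375 | 0.479 |
| 0.7 | 3 | 0.326 | 0.412 |

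If two independent answers must flip, a per-subject value of 0.3 needs √0.3 = 0.55 per answer, so these figures are towards the high end.

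**The case against.** **The surgeon's knowledge is inferred.** A reader might infer that the surgeon knows the dose and that the VRC sees results by dose. The text says only that site personnel obtain the assignment, and it does not say how VRC data are presented. The VRC charter, Imaging Charter, IRT manual and pharmacy manual are not available and may contain masking steps. This stands: the finding is that no masking is described, not that disclosure is shown.

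**Existing staff.** A reader might infer that present staff could do this without change. No pharmacist or separate preparer is named, and Protocol 6.2.2 allows the investigator access to stored product and a share in accountability. The double-blind phase 1 study and the IRT make masking plausible but do not establish it.

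**Masking may be weak.** The initial doses differ by a common ratio of 3, so the highest is 3 × 3 = 9 times the lowest, and the rater scores brightness directly. The solution is deep green, diluted doses may differ in shade or volume, and green urine is expected. This stands as a limit, but partial masking is still better than open disclosure.

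**Amount of data.** It would be wrong to say that every VRC decision rests on 3 ratings per dose. Only the first look does. Later looks accumulate to 15, each subject is rated at several times, and the VRC uses the totality of the data.

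**Stage and purpose.** This is an estimation-only phase 2 study. Amendment 2 describes adding subjects to one arm once it is determined to be optimal, which suggests, without proving it, that selection was advanced. For subjects enrolled after selection, dose masking has no purpose.

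**Conclusion.** The concern holds in a limited form. The plan leaves the rater of a subjective primary endpoint unmasked by default and puts the same role on the dose-selecting committee, while no stated procedure requires the rater to know the dose. This is worth correcting but is not a fatal flaw.

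The direction of any bias would follow the rater's expectation; its size cannot be derived from the documents. With an assumed 60% true success and 25% of No answers flipped at one dose, the observed rate is about 62.5% to 70%, and the chance of 3/3 about 24% to 34% against 22%. Taking the upper figures alone would overstate the case, because success needs Yes at two time points. A result of 3/3 is also not a decision threshold in the plan.

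**What to change.** In Protocol 6.3, for subjects randomized before the optimal dose is determined, state that the IRT dose assignment goes only to the site personnel who prepare and administer the product. It is not disclosed to the rating surgeon until that subject's visualization form is complete, except for safety. Require the preparer to be someone other than the rater, and confirm that each site can meet this. If a manual or charter already provides masking, Section 6.3 should say so.

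Do not extend this to coded dose labels in the VRC. The committee needs dose order for its lower-dose tie rule, and dose identity for its rules on adding dose levels (Protocol 4.1).

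The cost is IRT access roles, a paragraph in the protocol and matching text in the pharmacy manual, including who may see accountability records. The report should acknowledge that masking is partial. If masking in the operating room proves impractical, a dose-masked re-read of the archived recordings is a possible supporting analysis, at the cost of a reader. Sample size, arms and schedule do not change.

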6.4 Investigational Product Compliance

IP will be administered intravenously at the study site by study site personnel. The exact date and time (in minutes) of IP administration will be documented.

6.5 Previous and Concomitant Treatment (Medication and Nonmedication Therapy)

6.5.1 Previous Medication

The investigator must record the use of all previous (from day -28 or informed consent date, whichever is later, prior to visit 2) treatment in the eCRF, both medication and nonmedication treatments.

6.5.2 Concomitant Medication

The investigator must record the use of all concomitant (any medication between visit 2 and follow-up [visit 3]) treatment in the eCRF, both medication and nonmedication treatments.

6.5.3 Prohibited Medication

The following concomitant medications will not be allowed from 48 hours prior to the IP administration until the completion of the surgical procedure:

- ICG unless used for anastomotic evaluation
- Other NIR-F imaging agents
- Diuretics
- Inhibitors for renal transporters defined by FDA (see [Appendix 12.6 List of Excluded Concomitant Medications])

A list of excluded concomitant medications is provided in [Appendix 12.6 List of Excluded Concomitant Medications].

6.5.4 Alternative Therapy for Visualization

If the investigator judges that anatomical visualization of ASP5354 is not sufficient for the subject at 30 minutes after administration, the investigator can proceed with surgery using other modalities for visualization.

6.6 Dose Modification

Since this is a single dose study, dose modification is not applicable.

6.7 Criteria for Continuation of Treatment

Not applicable, as ASP5354 is a single dose anatomical imaging agent and has no therapeutic indications.

7 STUDY PROCEDURES AND ASSESSMENTS

7.1 Efficacy Assessments

7.1.1 Primary Efficacy Assessments

7.1.1.1 Anatomical Visualization of the Index Ureter(s) Using ASP5354

The investigator will select the index ureter (i.e., right or/and left) before surgery. The incidence of anatomical visualization of ureter(s) will be assessed at approximately 10, 20, 30, 45 and 60 minutes postadministration of ASP5354, and then every 30 minutes thereafter and/or at the last time point before removal of visualization instruments (end of surgery) by the investigator intraoperatively using a binary “Yes or No” question on the ability to visualize the ureter: “Can the ureter be adequately visualized with NIR-F”?

- If the answer to the question 30 minutes after ASP5354 administration and at the end of surgery = Yes, then anatomical visualization of the index ureter(s) was a success.
- All other cases will be handled as “Not a success”.

If the anatomical visualization of the index ureter(s) was not assessed, “Not Done” will be entered in the eCRF. However, in the only case that the anatomical visualization of the index ureter(s) was not assessed at 30 minutes after ASP5354 administration, the answer will be imputed as follows:

- If the answer at the nearest time points before and after 30 minutes both = Yes, then the answer to the question 30 minutes after ASP5354 administration will be imputed as = Yes.
- If the answer at the nearest time points before and after 30 minutes both = No, then the answer to the question 30 minutes after ASP5354 administration will be imputed as = No.
- All other cases will be handled as “Not Done” at 30 minutes after ASP5354 administration, and imputing will not occur.

7.1.2 Exploratory Assessments

7.1.2.1 Intensity of Fluorescence

The intensity of fluorescence will be qualitatively assessed during surgery by the investigator, by direct examination of the ureter. A Likert Scale (0 = None, 1 = Mild, 2 = Moderate and 3 = Strong) will be used to determine the intensity of fluorescence at each time point. The contralateral ureter will also be visualized when feasible, per the investigators judgment, at similar time points.

7.1.2.2 Duration of Ureter Visualization

Intraoperative ureter fluorescence visualization will be assessed at approximately 10, 20, 30, 45 and 60 minutes postadministration of ASP5354, and then every 30 minutes thereafter and/or at the last time point before removal of visualization instruments (end of surgery). The duration of visualization of the index ureter(s) will be based on the result from the first positive visualized time point to the last positive visualized time point. Images will be captured on a bright field, NIR-F and overlay view (if available). The contralateral ureter will also be visualized when feasible, per the investigators judgment, at similar time points.

7.1.2.3 Signal Background Ratio

Fluorescence images will be captured and recorded during the entire surgery and archived. Images will be captured on a bright field, NIR-F and overlay view (if available). SBR will be calculated using fluorescence images at predose, approximately 10, 20, 30, 45 and 60 minutes postadministration of ASP5354, and then every 30 minutes thereafter and/or at the last time point before removal of visualization instruments (end of surgery), as follows [[Hoogstins et al, 2019](#)]:

$$\text{SBR} = \frac{\text{mean region of interest}}{\text{mean signal background}}$$

Additional detail will be provided in the Imaging Charter.

7.1.2.4 Binary Questions (Yes/No) for the Benefit of Visualization by ASP5354 during Surgery

The investigator will be asked the following questions:

- Was the location of the index ureter(s) as expected (Yes or No)?
- Did visualization of the index ureter(s) occur with white light at 30 minutes after ASP5354 administration (Yes or No)?
- Did visualization of the index ureter(s) occur with white light at the end of surgery (Yes or No)?
- Was NIR-F superior to white light in terms of visualization of the index ureter(s) (Yes or No)?
- Did the location of the ureter visualized by NIR-F alter the operative plan (Yes or No)?
- Were any ureter anomalies or abnormalities observed (Yes or No)?

7.1.2.5 Ability to Visualize the Contralateral Ureter When Amenable to Visualization

The contralateral ureter will be assessed using the same binary questions for anatomical visualization and Likert Scale, when feasible, per the investigator's judgment, at similar time points.

7.2 Safety Assessments

Study procedures and their timing are summarized in the Schedule of Assessments [Table 1]. Protocol waivers or exemptions are not allowed.

Procedures conducted as part of a subject's routine clinical management (i.e., standard of care) obtained before signing the ICF may be utilized for screening or baseline purposes, provided the procedures met the protocol-specified criteria and were performed within the time frame, as defined in the Schedule of Assessments [Table 1].

